6.2 Secondary Effectiveness Endpoints

Secondary effectiveness endpoints are:

- a) The mean improvement in ODI from baseline to 3 years post treatment
- b) The mean improvement in ODI from baseline to 4 years post treatment
- c) The mean reduction from baseline VAS in patient reported pain score (10-point VAS-based numeric pain score) to each timepoint

- d) The number and proportion of subjects in each quartile ($\leq 24\%$ or less, 25-49%, 50-74%, and 75-100%) for percent pain score reduction in low back pain from baseline at each timepoint
- e) Responder rates for ODI: proportion of subjects who achieve ≥ 10 -Point, ≥ 15 -point and ≥ 20 -point reduction in ODI from baseline for each timepoint
- f) Responder rates for pain rating: proportion of subjects who achieve a ≥ 2.0 -point reduction in pain score from baseline for each timepoint
- g) Composite responder rate at each timepoint defined as:
 - 1) ODI decrease of ≥ 15
 - 2) NPS decrease of ≥ 2
- h) Composite responder rate at each timepoint defined as:
 - 1) ODI decrease of ≥ 15
 - 2) NPS decrease of greater than 50%
- i) Composite endpoint of long-term treatment success at each timepoint defined as:
 - 1) ODI decrease of ≥ 15
 - 2) NPS decrease of ≥ 2
 - 3) No injections for the same low back pain etiology and location as treatment location
 - 4) No pain intervention or surgery for the same low back pain etiology and location as treatment location
- j) The number and proportion of subjects with surgical interventions for low back pain of the same treatment region post the Intratect procedure at each timepoint
- k) The number and proportion of subjects actively utilizing (defined as $>25\%$ of total dosage in 30 days prior to study visit) opioids for low back pain of the same treatment region at each timepoint
- l) The number and proportion of subjects utilizing injections since the last study visit for low back pain of the same treatment region at each timepoint
- m) Work impact: number of missed workdays in past 30 days at each timepoint and number of days in bed in past 30 days
- n) Patient satisfaction with the Intratect Procedure at each timepoint

Ongoing safety will be evaluated at each time. SAEs potentially related to the procedure, device, or the spine will be reported and evaluated for relatedness.

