- The full cohort (N=47) was followed for 12 months post BVN ablation and improvements in pain and function remained significant.¹⁵ Forty-five (N=45) (95.7%) subjects completed a 12-month follow-up visit. Mean reduction in ODI at 12 months was 32.31 ± 14.07 ($p<0.001$) with 88.89% (40/45) patients reporting a ≥ 15 point ODI decrease at 12 months. Mean VAS pain score decrease was 4.31 ± 2.51 at 12 months ($p<0.001$) and more than 68% reported a 50% reduction in VAS pain scale. Minimally invasive RF ablation of the BVN demonstrated a significant improvement in pain and function in this population of real-world patients with chronic vertebrogenic-related LBP out to 12 months.¹⁵

The purpose of this study is to measure the long-term effectiveness outcomes at 3+, 4 and 5 years post treatment in subjects treated with the Intratect Procedure in the original A Prospective, Open-Label, Single-Arm Study of Intraosseous Basivertebral Nerve Ablation for the Treatment of Chronic Low Back Pain Single-Arm described above in section 3.3.

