5.1 Study Visits

Participants in the study will have three (3) study visits over a period of up to 3+ years based on the timing of their Intracept procedure. Study visits will be conducted via telephone by an independent CRA. Participants will provide verbal informed consent and then answer study questions via telephone study visits at 3+ years, 4 years, and 5 years post Intracept Procedure.

Study subjects who received treatment in the original CLBP Single-Arm Study are eligible to participate in this long-term follow-up data collection. Each study site will make initial contact with the prior study subject and discuss the follow-up study to discern if the subject is interested in participating. The same unique subject ID number used in the CLBP Single-Arm Study will be assigned to the subject. Study participant logs will include subject ID, date(s) of contact and date of agreement/declination to participate and will be maintained by the study site and independent CRA.

Upon subject agreement to participate in the study, the site CRC will forward subject contact information to the independent CRA who will contact the subjects, obtain verbal informed consent, and schedule the telephone study visit. The independent CRA will conduct the telephone study visit, be responsible for the collection of all data elements, and enter data into the designated clinical database.

Study Exit

Subjects will be considered to have completed the study after the 5-year follow-up visit is complete.

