5.2 Study Withdrawal/Termination

A subject may withdraw from the study at any time if he/she no longer wishes to participate. If subjects elect to withdraw or is terminated from the study, the independent CRA should inquire about the reason and document details accordingly on the study completion CRF.

If a subject does not respond to at least three documented contact attempts such that the follow-up visit does not occur, the visit will be documented as a "missed visit". Subjects who miss a follow-up visit should still be contacted again for their next scheduled study visit. It is important that continued attempts be made to re-establish contact at subsequent study visits. A subject should not be deemed lost to follow-up and withdrawn from the study until the independent CRA has documented sufficient efforts at achieving subject contact or until the 5-year follow-up study visit window closes for the last subject who received the Intracept procedure.

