8.5 Injections & Interventions

Patient-reported injections and interventions (i.e. RF ablations) for low back pain since the Intratect procedure or last study visit will be collected. Date, type, and location on back of each injection or intervention will be recorded.

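### Endpoint 6.2(l) counts injections over unequal look-backs, so the proportion is expected to fall from the first call to year 4 even if use is constant

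*Combined protocol and SAP*

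**What the plan says.** The combined protocol and SAP describes the look-back for injections in three places.

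- Section 6.2, item (l), the endpoint that will be reported: "The number and proportion of subjects utilizing injections since the last study visit for low back pain of the same treatment region at each timepoint".
- Section 8.5, the assessment: injections and interventions "since the Intratect procedure or last study visit will be collected. Date, type, and location on back of each injection or intervention will be recorded".
- Section 1 (Synopsis, efficacy assessments): injections over the preceding 12 months, collected at each telephone visit.

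The visit times come from two further sections. Section 3.3 says of the original study that "The full cohort (N=47) was followed for 12 months post BVN ablation", and that "Forty-five (N=45) (95.7%) subjects completed a 12-month follow-up visit". It describes no later visit. Under section 5.1, subjects then "answer study questions via telephone study visits at 3+ years, 4 years, and 5 years post Intracept Procedure".

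Missed visits are allowed. Section 5.2 says "Subjects who miss a follow-up visit should still be contacted again for their next scheduled study visit".

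Section 7.1 plans descriptive statistics for the secondary endpoints (for categories, number and percentage), on observed values without imputation. It does not mention the length of the look-back.

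**The concern.** The three figures for item (l) carry the same label but cover different amounts of patient time. A subject is more likely to have had at least one injection in a long interval than in a short one. Here the longest interval comes first.

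The study asks whether benefit lasts. If the proportion needing injections drops between the first call and year 4, a reader will naturally take it as a declining need for re-treatment. Unequal look-back can produce that pattern with no change in use, and it errs in the favourable direction. The endpoint is descriptive, so no test or model will reveal the problem. The year-5 figure is also affected, because it mixes look-backs of different lengths whenever some subjects missed year 4.

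**Working it through.** **Look-back lengths.** Let v be the month of the first call, with v at least 36, and take year 4 and year 5 as months 48 and 60.

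- First call: v − 12, so 24 months or more. Counted from the procedure, as 8.5 permits, it is v, so 36 months or more. For the two of 47 subjects without a 12-month visit, the look-back is longer than v − 12.
- Year 4, for a subject who had the first call: 48 − v, so 12 months or less.
- Year 5, for a subject who had the year-4 call: 60 − 48 = 12 months.
- Year 5, for a subject who missed only year 4: 60 − v, so 24 months or less.
- Year 4, for a subject who missed the first call: 48 − 12 = 36 months.

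These lengths are nominal. A late year-4 or year-5 call would change them.

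**Expected proportions under constant use.** The documents give no injection rate for this cohort, so the 12-month probability p is an assumption and is shown as a range. With a constant rate common to all subjects, the probability of at least one injection in t months is 1 − (1 − p)^(t/12).

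| Assumed p | First call, 24 months | Year 4, 12 months | First call if counted from procedure, 36 months |
|---|---|---|---|
| 5% | 1 − 0.95² = 9.8% | 5.0% | 14.3% |
| 10% | 1 − 0.90² = 19.0% | 10.0% | 27.1% |
| 15% | 1 − 0.85² = 27.8% | 15.0% | 1 − 0.85³ = 38.6% |

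At 10% and 45 subjects, the expected counts are 45 × 0.190 = 8.6 at the first call and 45 × 0.100 = 4.5 at year 4.

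**Late first call.** If v = 42 (an assumption) and p = 10%, the look-backs are 30, 6 and 12 months. The expected series is 23.2%, 5.1%, 10.0%: a fall and then a rise, with use unchanged.

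**Repeat users.** Let the individual rate follow a gamma distribution with shape k and mean m per year. The probability of at least one injection in t years is 1 − (1 + mt/k)^(−k), with m chosen so that the one-year value is 10%. The 24-month value is then 17.5% at k = 0.5, 14.4% at k = 0.1 and 11.2% at k = 0.02, against 10% for 12 months. The fall shrinks as injections concentrate in fewer subjects, and would vanish if the same subjects had injections in every interval and the others had none.

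**Missed first call.** If 30% miss the 3+ year call and p = 10%, the year-4 proportion is 0.7 × 10.0% + 0.3 × 27.1% = 15.1%, against 19.0% at the first call. The fall is smaller but remains.

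**Missed year 4.** At p = 10%, a subject who missed only year 4 carries 1 − 0.9^(24/12) = 19.0% at year 5 if the first call was at month 36, or 1 − 0.9^(18/12) = 14.6% if it was at month 42. A subject seen at year 4 carries 10.0%.

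**With a common 12-month window.** Under constant use, the expected proportion is p at all three timepoints (10%, 10%, 10% at p = 10%).

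**The case against.** The strongest reply is that the synopsis already fixes the look-back at 12 months. If the forms follow it, the artefact does not arise. That is correct, but the synopsis contradicts both 6.2(l) and 8.5, and 6.2(l) is the definition of what is reported. The reply shows that the sponsor has a suitable window to hand; it does not show which passage governs.

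A second reply is that the fall is not guaranteed. This stands. A reader might infer that the reported rate must drop by construction. The documents do not support that: the drop is an expectation under constant use. Repeat users weaken it, and so do missed first calls, which section 5.2 allows just as it allows missed year-4 calls. With at most 47 subjects, chance could also hide or exaggerate it.

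A third reply is that visit windows may be defined in text that is not public. Section 4.4 is blacked out, and 5.2 refers to a window for the 5-year visit. The month-42 scenario is therefore illustration only. The 24-versus-12-month contrast needs no late call, because it follows from the 12-month visit and nominal calls at 36 and 48 months.

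Finally, item (l) is one of 14 secondary items, with no planned test between timepoints. Each injection is dated, so no information is lost. This stands as an argument about weight. It does not make the three percentages comparable as they are now defined.

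**Conclusion.** The point holds in a limited form. Followed as written, 6.2(l) compares a look-back of at least 24 months with one of 12 months or less and then one of about 12, with no allowance for the difference. Under constant use at an assumed 5% to 15% a year, the first-call proportion is expected to be a little under twice the year-4 proportion (9.8% versus 5.0% up to 27.8% versus 15.0%). Counting the first call from the procedure widens the gap; heterogeneity between subjects and missed first calls narrow it.

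The result rests on three assumptions: that 6.2(l) governs rather than the synopsis, that no original-study visit took place after month 12, and that the annual rate lies in the range shown. The issue is modest. It affects how one secondary, descriptive series is read, and it leaves the primary ODI endpoint and all planned tests untouched. A reader might infer that injection results from this study cannot be used; the recorded dates show otherwise. It is still worth correcting, because the series bears on durability and the expected error is favourable.

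**What to change.** Reconcile the synopsis, 6.2(l) and 8.5 so that all three state the same look-back for reporting. Then define 6.2(l) along these lines:

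> Number and proportion of subjects with at least one injection for low back pain of the same treatment region during the 12 months before each timepoint (months 25–36, 37–48 and 49–60 after the procedure), assigned by injection date. The denominator is subjects whose completed contacts cover the whole window.

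The denominator rule should say how two cases are handled: a call made before its window closes, and a subject who missed year 4 but gave dated information at year 5. It must also fit the observed-values-only rule in 7.1.

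Keep collecting every injection since the previous contact. Show those outside the windows in a listing, as a cumulative proportion since the procedure, or as a rate per person-year. If the rate counts subjects rather than injections, person-time should stop at the first injection.

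The cost is a few sentences and simple programming, with no new data, since 8.5 already records dates. One small loss is that injections in months 13–24 leave the year-3 proportion and appear only in the supplementary display.

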7 STATISTICAL ANALYSIS

7.1 Statistical Methods

The mean change in ODI from baseline to five years is the primary endpoint for this study. Baseline is defined as the last non-missing assessment at or before the baseline visit and prior to the Intratect treatment from the original CLBP Single-Arm Study.

Statistical tests will be two-sided and will be performed at the 0.05 level of significance. Statistical differences will be tested using Student's t-tests. An analysis of covariance (ANCOVA) will also be performed using baseline ODI measurements for the primary endpoint. Baseline NPS will be used as a covariate for the secondary pain reduction endpoint. No other planned analyses will include covariates.

Descriptive statistics will be used for secondary endpoints and will include the number and percentage of subjects in each category. For continuous parameters, descriptive statistics will include n (number of subjects), mean, SD, median, minimum, maximum, and confidence intervals.

Results will be for observed values only. No imputations will be made for missing data.

8 DESCRIPTION OF STUDY ASSESSMENTS

8.1 Oswestry Disability Index

The Oswestry Disability Index (ODI) is a validated questionnaire of low back pain-related disability.¹⁶ It assesses the impact of low back pain on activities of daily living and participation and includes 10 questions. It is scored on a scale of 0 (no disability) to 100 (complete disability), with categories of 0-20 (minimal disability), 21-40 (moderate disability), 41-60 (severe disability), 61-80 (crippling back pain), and 81-100 (bed-bound or exaggerating). The minimally clinically important difference for this tool is considered to be 10 points.¹⁷ For the purposes of this study, this will be administered over the phone.

8.2 Pain Rating Scale for Back Pain Assessment

The numeric pain score (NPS) that will be used for this study is a 10-point numeric scale based on the Visual Analogue Scale (VAS) pain rating questionnaire,¹⁸ with 0 being no pain and 10 being worst imaginable pain. Respondents are asked to indicate what number on the scale corresponds to their perceived level of pain in their low back. Subjects will be specifically instructed to report their level of low back pain as an average for the last seven days. Studies have shown that a minimally clinically important difference in VAS is considered to be approximately 1.5 cm.¹⁹ For the purposes of this study, this will be administered over the phone by asking subjects to rate their average pain in the past seven days on a scale of 1 to 10, with 0 being no pain and 10 being worst pain imaginable.

8.3 Patient Satisfaction

Satisfaction will be assessed with a short, non-validated questionnaire about degree of improvement, satisfaction with treatment, and willingness to repeat the treatment for the same outcome.

8.4 Opioid Medications

Patient-reported opioid usage for CLBP will be captured. Medication type, prescribed dosage, and average daily dose for the last 30 days will be documented on the source document worksheet.

8.5 Injections & Interventions

Patient-reported injections and interventions (i.e. RF ablations) for low back pain since the Intratect procedure or last study visit will be collected. Date, type, and location on back of each injection or intervention will be recorded.

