8.7 Injections, Interventions, and Surgeries Adjudication

An independent physician will review all available medical records and radiologic images obtained by the study site to determine diagnosis (pain location, etiology, and nature) resulting in an intervention (procedure and/or injections) or surgery. All interventions and surgeries will be adjudicated as either a treatment failure (ongoing or exacerbated CLBP of similar location, anatomy, etiology /pain source, and nature/severity to the pre-Intracept treatment pain) or not related (different location, anatomy, etiology/pain source, or nature/severity). The independent physician will also review all medical records and radiologic images obtained by the study site to determine or evaluate reported adverse events.

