10.3 Confidentiality

Subject medical information obtained for this study is confidential, and disclosure to third parties other than those authorized for the study and IRB regulatory oversight is prohibited. Subjects will only be identified by the unique study ID assigned to them for the study. Data will be de-identified in a manner compliant with HIPAA regulations.

Upon the subject's consent to participate, the independent CRA will conduct the telephone study visits. All study visit data is provided directly by the subject during the telephonic study visit. A release of medical records will be obtained from the subject prior to accessing subject's medical records for adverse event and additional pain interventions / surgeries review and adjudication review .

Data generated by this study must be available for inspection upon request by representatives of the FDA, national and local health authorities, the Sponsor or its designee, and the IRB for the study site, if appropriate.

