10.4 Source Documents

Source data includes all information, such as original records of clinical findings, observations, or other activities in a clinical study necessary for the reconstruction and evaluation of the study. Source data for this study are the patient-reported outcomes and medication use which may be recorded on the source document worksheets by the independent CRA and then entered into the designated clinical database; these will serve as the primary data collection instruments for this study.

The assigned, study-wide independent CRA will be responsible for conducting the three-, four- and five-year telephone visits, collecting the requested data at the visits, and timely completion and submission of data into the clinical database. Medical records received via medical release will be considered the source data for injections, medications, additional pain interventions or surgeries, and adverse events. The clinical database will be considered the source data for any data collected verbally from the study subject and entered directly into the clinical database.

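### Later injections and interventions are found by patient report with no stated records check for subjects who report none, so re-treatment rates are probably understated and composite success probably overstated

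*Combined protocol and SAP*

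**What the plan says.** **Capture.** Section 8.5 states: "Patient-reported injections and interventions (i.e. RF ablations) for low back pain since the Intratect procedure or last study visit will be collected". Section 10.3 adds: "All study visit data is provided directly by the subject during the telephonic study visit". Section 8.6 says that back surgeries are documented over the same period, without naming who supplies the information.

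**Records.** Section 10.3 also says: "A release of medical records will be obtained from the subject prior to accessing subject's medical records". It gives the purpose as review and adjudication of adverse events and of further pain interventions or surgeries. Section 10.4 says: "Medical records received via medical release will be considered the source data for injections, medications, additional pain interventions or surgeries, and adverse events".

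**Adjudication.** Section 8.7 says: "An independent physician will review all available medical records and radiologic images obtained by the study site". It continues: "All interventions and surgeries will be adjudicated as either a treatment failure", the alternative being not related. Injections are among the events covered.

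**Endpoints (6.2).** Item (l) is "The number and proportion of subjects utilizing injections since the last study visit for low back pain of the same treatment region at each timepoint". Item (j) counts surgery for pain in the treated region. Composite (i) needs an ODI fall of at least 15, an NPS fall of at least 2, and no injection, pain intervention or surgery for pain of the same etiology and location. All are secondary; 7.1 assigns descriptive statistics to secondary endpoints, on observed values only.

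**Look-back.** The synopsis lists injections over the past 12 months. Items 6.2(l) and 8.5 run from the last study visit, and 8.5 also names the procedure as a starting point.

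**The concern.** Whether a re-treatment is counted depends first on the subject remembering it and mentioning it by telephone. A reported event can be looked up and adjudicated. A forgotten one triggers nothing that the text describes. The second source is therefore applied where an event is already known and not, as far as the text shows, where one may have been missed.

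This matters more than usual because there is no comparator arm in which the same under-counting would cancel. Items (i), (j) and (l) also each carry a region, location or etiology filter, and no unfiltered rate is planned, so a reader cannot see how many lumbar procedures were set aside. At stake is how credible the durability claim is: few re-treatments, and a high share with long-term success.

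**Working it through.** The documents give no re-treatment rate, recall accuracy or adjudication error rate, so there is no stated figure to reproduce. The text settles steps 1 to 3; steps 4 to 6 use assumed values.

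**1. Routes by which an event can enter the data.**
- Reported by the subject: collected under 8.5, records released under 10.3, adjudicated under 8.7.
- Not reported: 8.5 does not capture it. Section 10.4 covers only records that were received, and 8.7 only records that are available and were obtained. Neither says whose records are requested.

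**2. Look-back at the first call.** Section 3.3 describes original follow-up to 12 months; 5.1 puts the first call at 3+ years.
- From the last study visit: 36 − 12 = 24 months or more.
- From the procedure: 36 months or more.
- Under the synopsis: 12 months for injections. For a call at month 36, injections in months 12 to 24 would not be asked about.
- At the 4- and 5-year calls: about 12 months, if the previous visit took place.

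**3. Direction of adjudication.** A reported event is either kept or classed as not related, so among reported events the adjudicated count cannot exceed the raw count. Treatment failure lists similar features joined by 'and'; not related lists differences joined by 'or', so one difference appears enough. There is no undetermined class and no rule for missing records.

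**4. Recall loss alone.** Observed rate = true rate × recall sensitivity. Assume a true same-region rate of 20% and sensitivity of 70% to 90%.
- 0.20 × 0.7 = 14%
- 0.20 × 0.9 = 18%

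At N=47 the true count is 9.4 subjects, and 6.6 to 8.5 would be seen.

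**5. Errors in both directions.** Observed rate = p·s·(1 − a) + u·s·b, where
- p = share with same-pain re-treatment
- u = share with only unrelated low-back procedures
- s = probability that an event is captured
- a = probability that a related event is wrongly classed as not related
- b = probability that an unrelated event is wrongly kept as treatment failure

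| p | u | s | a | b | Observed | Bias (points) |
|---|---|---|---|---|---|---|
| 20% | 10% | 0.8 | 0.1 | 0 | 14.4% | −5.6 |
| 30% | 10% | 0.7 | 0.2 | 0 | 16.8% | −13.2 |
| 10% | 10% | 0.9 | 0.1 | 0.2 | 9.9% | −0.1 |
| 10% | 10% | 1 | 0 | 0.2 | 12.0% | +2.0 |

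With b = 0 the bias is never positive. With b = 0.2 it can change sign.

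**6. Composite (i).** A missed event changes the result only if the subject also meets the ODI and NPS criteria. Rise = p·r·m, where r is the share of re-treated subjects who otherwise qualify and m the share of related events missed.
- 0.20 × 0.5 × 0.3 = 3.0 points
- Low end: 0.10 × 0.25 × 0.1 = 0.25 points
- High end: 0.30 × 0.75 × 0.3 = 6.75 points
- Per subject: 1/47 = 2.1 points; 1/40 = 2.5 points (40 is an assumed number of participants)

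**The case against.** The strongest reply is that the plan does not rest on recall alone. Section 10.4 makes medical records source data, 8.7 has an independent physician review what the site obtained, and 10.3 does not restrict the release to subjects who report an event. Records obtained for one reported event could reveal another. Section 4.4 is redacted, and sections 10.6 and 11 are not in the text reviewed. This stands to the extent that a reader cannot conclude that a forgotten event is never added. What can be said is that no visible sentence provides for adding it.

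A reader might also infer that every error favours the device. The documents do not support that. An unrelated procedure kept as treatment failure, or an event over-reported or placed in the wrong region or period, raises the rate and lowers composite success; the last row of the table shows the sign reversing.

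A third tempting reading treats everything that adjudication removes as under-counting. Composite (i) is defined by same etiology and location, so correctly removing an unrelated procedure is the endpoint working as defined. Only wrongful removal is bias. Items (j) and (l) are defined by treated region and are not expressly tied to the 8.7 result, so an effect of adjudication on them is an inference; their exposure to missed reports is not.

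Finally, these are secondary, descriptive endpoints, and the later calls have a shorter look-back. Both points limit the importance of the concern without removing it.

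**Conclusion.** The concern holds in a limited form. First identification is by patient report, no records check is stated for subjects who report nothing, and the wording of 8.7 appears to make not related easier to reach than treatment failure. The likely net bias is toward lower rates in (j) and (l), and toward higher success on (i) among subjects who also meet its ODI and NPS criteria. It is not certain, because errors in the other direction are possible.

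Recall loss alone would turn a true 20% into 14% to 18%, and each missed event in an otherwise qualifying subject is worth 2.1 points at N=47. The true rate and the recall sensitivity are assumptions, not document figures. The primary endpoint, mean ODI change to 5 years, uses none of these data. Separately, the synopsis contradicts 6.2(l) and 8.5 on the injection look-back, and the passages must be reconciled.

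**What to change.** 1. **Sections 8.5, 8.6 and 10.3.** Request the medical-record release from every participant at the first call. Have the existing site CRCs check the site's own charts for lumbar injections, interventions and surgeries since the procedure, for all participants including those who report none. Send events found this way through 8.7, and count those that qualify in (i), (j) and (l).
2. **Section 6.2.** Beside (i), (j) and (l), report a supportive rate that counts every lumbar injection, intervention or surgery collected, whatever its region or adjudication.
3. **Synopsis, 6.2(l) and 8.5.** Reconcile the injection look-back so that one period applies throughout.

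The cost is a few protocol sentences, a chart check of at most 47 subjects at two sites, and an extra table column. The downsides are some CRC time, rates that may look slightly less favourable, and incomplete cover: care given elsewhere may still be missed, so the chart check reduces the gap without closing it.
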